105 first dose will be taken at the start of enrollment if the subject is on the 3rd day of active bleeding 106 or if not bleeding, on day 3 of the next bleeding episode. The study will be conducted at Oregon Health & Science University (OHSU) in Portland, Oregon 107 108 Each subject's involvement will be up to approximately 60 days as study drug will not be 109 initiated at the time of enrollment unless they are experiencing bleeding/spotting that day and 110 the two prior days to enrollment. Study drug will be started on the 3rd day of an active bleeding 111 episode. If no active bleeding episodes happen in the first 30 days from enrollment then the 112 participant will be withdrawn from the study. The study will require up to 3 in-person study visits 113 [screening (V1), enrollment (V2), and a close out visit or study exit (V3)], as well as a daily 114 response to a text or email message about bleeding and use of study medication. Additional 115 116 phone and email contact may occur with the participant to ensure clarity of diary entry or completion or to ensure drug initiation and compliance. The electronic diary only takes a few 117 118 seconds to complete ...

119

Eligibility: 120

- 121 Inclusion:
- 122

125 126

134

136

137

- English speaking women 15-45 years of age currently using the ENG implant who have experienced frequent or prolonged bleeding while using the device: 123 124
 - To be eligible, women will need to have >7 days of continuous bleeding/spotting 0 in the last 30 days, OR 2 or more episodes of bleeding/spotting in the last 30 davs.
- 127 Implant use for at least 30 days prior to screening visit.
- 128 Willing to continue using the implant for at least 30 days from study enrollment.
- Access to a reliable cell phone and must be willing to receive and respond to a daily text 129 or email message to assess bleeding and use of study drug 130
- Implant must be palpable to prove that an ENG implant is in place at time of screening 131 132 and enrollment. 133
 - Negative gonorrhea/chlamydia screening performed at screening visit •

135 Exclusion criteria:

- Postpartum within six months •
- Post-abortion within six weeks •
- Currently pregnant 138 •
- Currently breast-feeding (to be eligible, must be 4-6 weeks from cessation of 139 140 breastfeeding)
- Undiagnosed abnormal uterine bleeding pre-dating placement of contraceptive implant 141 •
- 142 Bleeding dyscrasia •
- Anticoagulation use 143 •
- Active cervicitis 144 •

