183 The final visit will take place approximately 90 days after enrollment or at the time of study

- 184 withdrawal/exit. Repeat STI testing only if indicated by a change in partners during the study.
- 185 Vital signs will be performed and a review of bleeding diary, medications, AEs, and health
- 186 changes. A short satisfaction questionnaire will be performed. Participation is complete after
- this visit. Unused study drug will be retuned at these visits.
- 188

Details
 Informed consent Review medications Confirm implant use Physical exam with vitals (blood pressure, pulse, weight, height) Urine pregnancy test Review eligibility criteria Gonorrhea and chlamydia test Pap (if indicated) Basolino questionnaire

Visit 2– enrollment	 Review bleeding diary with staff Review medications Vitals (blood pressure, pulse, weight, height) Confirm implant use Receive placebo or study drug and instructions Review any health changes
Visit 3- end of study	 Urine pregnancy test if indicated Repeat Gonorrhea and chlamydia test if change in partner occurs during study. Review medications Return any unused medication Vitals (blood pressure, pulse, weight, height) Confirm implant use Review bleeding diary with staff Review health changes Exit guestionnaire

189

190 Description of intervention/study drug

191 Participants will be instructed to begin use of the study medication daily. A study coordinator

192 (SC) will prospectively follow electronic bleeding diaries at a minimum of three times weekly for

193 each individual study subject to ensure data integrity and correct day of drug initiation. Any

unused study drug will be counted and returned at the conclusion of the study.

195

Failure to complete the texting diary will prompt a phone call or email from the SC. If we are unable to reach a subject by phone, email, letter over a 2-week time period, their participation will be terminated. Any data obtained up to this point will be analyzed in accordance to with

intention to treat.

200

201 Study procedures and data collection other than side effects and AEs will last 30-days from 202 enrollment.

203

204 Compensation

Participants will be compensated up to \$250 for their participation in this study. Study visit compensation breakdown is as follows:

- 207
 Visit 1- Screening:
 \$50

 208
 Visit 2- Enrollment:
 \$50

 209
 Visit 3- Study end
 \$50

 210
 Diary Completion:
 \$100
- 211

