212 Subjects will only be compensated for the visits they complete. For example, if a subject

withdraws after visit 2, they will only be compensated for those two visits (\$50 + \$50).

214 Diary compensation

215 Diary completion is defined as responding to 1 daily text message per day. A subject can miss

- up to 2 days of responses in the up to 60-day study period and still receive diary compensation.
- 217 If a subject misses 3 or more days of diary entry in a given 30 days, they will not receive this

- compensation. Study coordinators will be tracking diary responses, and response rates. If a
- subject withdraws early from the study, they will only receive compensation for visits that they have completed and not the compensation for diary completion.
- 221

222223 Sample size

224 Our primary outcome is the total number of amenorrhea days in a 30-day reference between 225 curcumin and placebo groups. Our prior tamoxifen study demonstrated a 6-day difference in 226 overall amenorrhea days in the first 30-day reference period.

227

Based on our recent tamoxifen study, a sample size of 44 women allows us to demonstrate a 6day difference between groups; 80% power at an alpha 0.05 = 22 women per each group. To
account for drop out, we have increased the sample size by approximately 30% for a total
sample size of 58.

231 232

233 Study drug

- 234 Curcumin an active ingredient in the spice Tumeric is a natural polyphenol. It is purported to
- have multiple health benefits mostly based in its anti-inflammatory and anti-oxidant properties.
- 236 Curcumin dosing has been demonstrated to be well tolerated in humans up to 12,000mg/day
- but dosing as a cancer treatment adjunct or as an autoimmune therapy are in the 400-
- 600mg/day range [1,2]. In general, subjects seem to experience no side effects from curcumin
- but in a dose escalation study to determine safety and tolerability, 7 of 34 subjects experienced
- 240 headache, rash, and yellow stool. At higher doses, some nausea and diarrhea have also been
- 241 reported. Curcumin may have a beneficial effect on cholesterol and triglycerides. Curcumin has
- 242 poor bioavailability and combining it with piperine, a known bioenhancer derived from black
- 243 pepper, has been shown to improve curcumin bioavailability by 2000% [3]. However, curcumin
- without a bioenhancer has also demonstrated therapeutic impact in randomized controlled trials.

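### Does the increase from 44 to 58 women for drop-out fall short of the 80% power the plan states?

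*Combined protocol and SAP*

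**What the plan says.** The relevant text is in the Sample size section of the combined protocol and SAP. The effect comes from earlier work by the same team: "Our prior tamoxifen study demonstrated a 6-day difference in" amenorrhea days over the first 30-day period. From this the section concludes that "a sample size of 44 women allows us to demonstrate a 6day difference between groups", with "80% power at an alpha 0.05 = 22 women per each group". The drop-out sentence follows. To "account for drop out, we have increased the sample size by approximately 30% for a total" "sample size of 58".

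The section gives no expected drop-out rate, no standard deviation, and no statement of whether the test is one- or two-sided.

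Two other places bear on loss. Under Study design/Clinical Plan, a woman who does not bleed is withdrawn: "If no active bleeding episodes happen in the first 30 days from enrollment then the" participant leaves the study. Under Description of intervention/study drug, a woman who cannot be contacted over two weeks is terminated, but her data are kept: "Any data obtained up to this point will be analyzed in accordance to with" the intention-to-treat principle.

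**The concern.** To keep a required number of evaluable women, n, when a proportion d will be lost, the number to randomise is n/(1 − d). Multiplying by (1 + d) gives too few, and the gap widens as d grows. Here 44 × 1.3 rounds up to exactly 58, so the total looks like the product of the wrong formula. The only percentage in the sentence on drop-out is 30%, so it is natural to read it as the loss the trial is built to absorb.

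On that reading the trial would miss its stated power whenever loss reached 30%, and the team would think it could bear more loss than it can. The margin would also have to cover women who are randomised at the enrollment visit and then withdrawn because no bleeding episode occurs, as well as those lost to contact.

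**Working it through.** **Inputs from the Sample size section:** 44 women in total (22 per group), a 6-day difference, 80% power, alpha 0.05, an increase of approximately 30%, and a final total of 58. **Assumed, because not stated:** a two-sided test, power of exactly 80% at 44, and no primary-outcome data from any woman who is lost.

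**1. The plan's own figure.** 44 × 1.30 = 57.2, rounded up to 58. Per group, 22 × 1.30 = 28.6, rounded up to 29, and 2 × 29 = 58. The figure reproduces.

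**2. Is the described increase true?** 58/44 = 1.318, an increase of about 32%. Approximately 30% is a fair description.

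**3. What loss does 58 absorb?** 58 − 44 = 14 women, and 14/58 = 24.1%. In the other direction, 44/(1 − 0.24) = 57.9, rounded up to 58. The division formula therefore gives 58 for a loss of about 24%.

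**4. What if 30% were lost?** 58 × 0.70 = 40.6, about 41 women. Keeping 44 would need 44/0.70 = 62.9, so 63 women, or 64 with equal groups: 5 or 6 more.

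**5. Power at that loss.** With 80% power at 44, the normal approximation for n women is Φ(√(n/44) × (1.960 + 0.842) − 1.960). For the t-test, the standard deviation that gives 80% at 22 per group was solved for first (6.94 days; 7.10 by the normal approximation).

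| Women analysed | Normal | t-test |
|---|---|---|
| 44 (22 and 22) | 80.0% | 80.0% |
| 41 (20 and 21) | 77.2% | 77.0% |
| 40 (20 and 20) | 76.2% | 75.9% |

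If the 22 per group was itself rounded up from just above 21, power at 41 could be as high as about 79%. With no loss at all (29 per group) it is about 90%.

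**6. Comparison with the text.** The shortfall in steps 4 and 5 appears only if 30% is the expected loss. The plan uses 30% for the increase in the sample and attaches 80% power to 44 women. It makes no claim about power after a 30% loss, so these steps contradict nothing it states.

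**The case for a change.** The strongest argument for the concern is about how the sentence will be read. Because 30% is the only number linked to drop-out, a reader may take it as the tolerated loss, and that reader would be wrong by about 6 percentage points (30% against 24.1%). The limit of 24.1% needs no standard deviation and is not in doubt. Intention-to-treat analysis is also an incomplete answer: the outcome is a count over 30 days, no method is given for scoring a partial diary, and a woman who never starts the drug has no treatment period to score. The plan does not say whether such women are meant to fall within the drop-out allowance.

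What stands is that the expected drop-out rate is not stated and the sentence can be misread. That does not make 58 a miscalculation. For women who never start, the documents give no rate, so nothing shows that a margin of 14 is too small or was meant to exclude them. The power figures at 30% loss also count every lost woman as contributing nothing, which is the pessimistic case given that partial data are to be analysed. A sentence stating the 24% limit would be harmless. However, it would correct no figure and would leave 58 in place. Adding a standard deviation of about 7 days would be circular, because that value was obtained by assuming the 80% power it would then appear to support.

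**Conclusion.** The concern does not hold. It treats an inflation factor as a drop-out rate that the plan never gives. The increase is described accurately, the 80% is attached to the 44 women it belongs to, and 58 is the right total for a loss of up to 14 women, or 24.1%.

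Even if 30% were lost, power would fall by about 3 to 4 points, to roughly 76–77%, under an assumed two-sided test, exactly 80% at 44, and no contribution from lost women. What remains is an unstated planning assumption. Stating it would not change the sample size, the analysis or the conclusions drawn from the trial. This verdict would change only if the documents gave 30% as the expected loss, and they do not.
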